5.2 Intercurrent events

The following intercurrent events are defined to describe the treatment effect that is targeted with the different estimand strategies described underneath.

- Treatment completion: This intercurrent event occurs either when a subject completes the period of the trial the subject consented to or is withdrawn from the trial due to tralokinumab becoming commercially available in their country. This intercurrent event is introduced mainly due to the extension amendment introduced in May 2021. Notably, it was not collected in the eCRF whether a subject withdrew due to not consenting to continue in the extension of the trial. Subsequently, an algorithm was built such that withdrawals close (17 days) to the country-specific closure date were classified as treatment completers instead of as having permanently discontinued IMP. See the ADRG for a complete algorithm defining treatment completion.
- **Permanent discontinuation of IMP:** This intercurrent event occurs when a subject is withdrawn from trial while under treatment. It can occur at the subjects' own initiative, at the discretion of the investigator or the sponsor, or if the subject is lost to follow-up:
 - **Due to lack of efficacy (LoE) or adverse event (AE):** This intercurrent event occurs when it is specified that the primary reason for withdrawal from trial while under treatment is due to either LoE, or AE. Of note, the reasons "withdrawal by subject", "lost to follow-up" and "other" were queried to ensure that the underlying reason was not LoE or AE.
 - Not due to LoE nor AE: the complement to the previously specified reasons.

5.3 **Baseline presentations**

Due to safety-related analyses specified for subjects coming from the LP0162-1334 trial in the protocol, baseline presentations will be specified where applicable for subjects from the LP0162-1334 trial.

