This hypothetical assumption applied to the imputation of missing data from subjects who either completed treatment (e.g. due to commercialization of tralokinumab in their country) or permanently discontinued IMP is strong. However, assuming that these subjects continued as if they had regressed to their within-subject mean is appropriate under this hypothetical sensitivity scenario as it attempts to estimate the proportion of responders under minimal influence of survival bias.

5.6.1.1.2.2 mNRI-MI with treatment adherence MI strategy (mNRI-MI-Hyp)

This sensitivity analysis seeks to estimate a lower bound of the response by estimating the response achieved without permanent discontinuation of IMP due to LoE or AE if all subjects who withdrew for other reasons had continued in the trial like they were before they dropped out.

The response at each scheduled visit will be calculated based on both observed and multiply imputed missing or unobserved assessment data, with those having permanently discontinue IMP due to LoE or AE prior to the analysed visit imputed as non-responders. Missing assessment data will be imputed using the same 2-step MI strategy (see section 5.6.1.1.2.3) as in the hMI sensitivity analysis. Permanent discontinuations of IMP due to LoE or AE of subjects who permanently discontinued IMP for other reasons or completed the trial will be imputed using the hypothetical treatment adherence MI strategy (see section 5.6.1.1.2.3) onto subjects who either completed treatment or permanently discontinued IMP for other reasons than LoE or AE after the time they discontinue.

This hypothetical scenario sets out to estimate a lower bound of efficacy by assuming that subjects who are either observed or imputed to permanently discontinue of IMP due to LoE or AE are perpetually considered non-responders. In dealing with subjects who drop-out early, it sets a strong assumption that regression-to-the-mean can be assumed when imputing assessment data. But in doing so, this sensitivity strategy targets the same underlying target of estimation established in trials of other similar drugs in AD long-term extension trials (2) where subjects have been non-responder imputed based only on observed permanent discontinuation of IMP due to LoE or AE, with assessment data imputed using last

observation carried forward. However, last observation carried forward will not be used as it is not appropriate, see e.g., "Fallacies of Last Observation Carried Forward" (3).

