
5.6.1.1.2.3 Imputation strategies

2-step MI strategy

A 2-step MI strategy will be employed to mitigate potential survival bias as reasoned above. MI of missing data and data unobserved after intercurrent events can be used by the different sensitivity analyses per the need of the various estimation requirements:

- Data up until the Week 56 visit will be imputed using a Full Conditional Specification gaussian regression-based MI model adjusting for previous visit (if planned visit exist), next visit (if planned visit exist), parent trial, and region. If the score being imputed is ordinal or binary, an ordinal logistic regression model will be used instead. The assumption here is that the data used in the MI regression model are robust enough.
- 2. Data after the Week 56 visit will be imputed using a within-subject non-parametric approach leveraging the proportion of response each subject has achieved estimated using linear interpolation across observed and (in the previous step) imputed scores. This proportion of response could also be called a within-subject AUC of days in response. The imputation will be derived in the following 3 steps:
 - 1. All days between observed and imputed visits will be imputed on the assessment's scale by using linear interpolation between visits. For binary and ordinal scores, the imputed value will be rounded.
 - 2. Then all days will be transformed into the binary endpoint and an average of those 1s (response) and 0s (non-response) going one year back (but not further back than the Week 16 visit) will be the AUC of days in response. This assumes that from the Week 16 visit that all subjects have regressed to their individual mean while under long-term treatment with tralokinumab (due to the safety follow-up between parent trials and ECZTEND with no dosing).
 - 3. An imputed response at each day, including planned visits, after the intercurrent event will then be drawn from the Bernoulli distribution by using the AUC of days in response as a probability.

Hypothetical treatment adherence MI strategy (Hyp)

MI of treatment adherence status at end of the treatment period, t_{EoTrt} , for subjects experiencing an intercurrent event, at time t_{ICE} , will be imputed based on the semi-parametric Cox proportional hazard model. The model will provide an estimated probability $\hat{p}(t_{EoTrt},$ region, parent trial) of being on treatment at the later time t_{EoTrt} conditional on being on

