treatment at the earlier time t_{ICE} in the hypothetical scenario where permanent discontinuation of IMP due to pandemic restrictions would not occur. The conditional probability \hat{p} will be calculated as the estimated survival function evaluated at t_{EoTrt} divided by the same function evaluated at time t_{ICE} (with $t_{ICE} < t_{EoTrt}$) and imputed using random draws from an exponential distribution with rate \hat{p} . For specific regional analyses, t_{EoTrt} may vary depending on the scarcity of data at the end the treatment period, but for summaries of the main populations Week 264 will be used.

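### The mNRI-MI-Hyp step uses a probability of staying on treatment as an exponential rate, with no time unit or mapping rule, so its lower bound cannot be reproduced from the SAP

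*SAP*

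**What the plan says.** SAP 5.6.1.1.2.2 defines mNRI-MI-Hyp. Its purpose is stated as "This hypothetical scenario sets out to estimate a lower bound of efficacy". At each visit it treats as non-responders "those having permanently discontinue IMP due to LoE or AE prior to the analysed visit imputed as non-responders". For subjects who did not stop for lack of efficacy (LoE) or an adverse event (AE), such a stop is imputed. The text refers to "Permanent discontinuations of IMP due to LoE or AE of subjects who permanently discontinued IMP for other reasons or completed the trial" and sends the reader to SAP 5.6.1.1.2.3 for the method.

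That section describes "MI of treatment adherence status at end of the treatment period" for subjects with an intercurrent event. A Cox model with region and parent trial supplies the probability p of being on treatment at t_EoTrt given being on treatment at t_ICE, that is p = S(t_EoTrt)/S(t_ICE). The setting is described as one "in the hypothetical scenario where permanent discontinuation of IMP due to pandemic restrictions would not occur". Status is then "imputed using random draws from an exponential distribution with rate" p. For t_EoTrt, "for summaries of the main populations Week 264 will be used".

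SAP Section 6, Panel 5, makes this one of the two analyses that replace the protocol's non-responder analysis of the secondary endpoints. The SAP Introduction says the level of detail should let a reader reproduce every analysis.

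**The concern.** The rate of an exponential distribution is a hazard per unit of time. Here p is a unitless probability of staying. Used as a rate, a larger p gives an earlier draw, so the subjects whom the Cox model rates most likely to stay are the first to be imputed as leaving.

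Three things needed to run the step are missing: the time unit of the draw, the rule from draw to status, and the rule from draw to date. SAP 5.6.1.1.2.3 speaks of status at the end of treatment, while SAP 5.6.1.1.2.2 has to know whether the stop came before each analysed visit. The ADRG is cited for the treatment-completion algorithm (SAP 5.2) and for the PCS criteria (SAP 5.8.2 and 5.8.4), not for this step.

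Two related gaps sit in the same paragraph. The Cox event can be inferred as an LoE/AE stop, but it is not stated and neither is the censoring. The hypothetical scenario also names only pandemic withdrawals, while SAP 5.6.1.1.2.2 applies the strategy to all treatment completers and to every other-reason withdrawal, which SAP 5.2 defines as "the complement to the previously specified reasons".

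At stake is the calibration of the lower bound for both secondary endpoints, in the total population and in each treatment-history group (SAP 5.6.1.1.3).

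**Working it through.** The documents give no value of p and no figure for this step, so there is nothing to reproduce. The check is whether the stated draw returns p.

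**Inputs.** From the SAP: p = S(t_EoTrt)/S(t_ICE), an exponential draw X with rate p, and t_EoTrt = Week 264. Assumed: p = 0.95, 0.90, 0.70, 0.50. Also assumed: an early stop at Week 140 (264 − 140 = 124 weeks left, or 124/52.18 = 2.376 years) and a late stop at Week 244 (20 weeks left, or 0.383 years).

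**Formula.** P(X > u) = exp(−p·u).

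| Reading of the draw | Imputed retention at Week 264 | p = 0.95 | 0.90 | 0.70 | 0.50 |
|---|---|---|---|---|---|
| Time, unit = remaining interval | exp(−p) | 0.39 | 0.41 | 0.50 | 0.61 |
| Retained if X < 1 | 1 − exp(−p) | 0.61 | 0.59 | 0.50 | 0.39 |
| Time in years, 124 weeks left | exp(−2.376p) | 0.10 | 0.12 | 0.19 | 0.30 |
| Time in years, 20 weeks left | exp(−0.383p) | 0.695 | 0.708 | 0.765 | 0.826 |
| Time in weeks, 20 weeks left | exp(−20p) | <0.0001 | <0.0001 | <0.0001 | <0.0001 |

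- **Interval unit.** The order is reversed. exp(−p) = p only at p = 0.567, so dropout is overstated above that value and understated below it.
- **Retained if X < 1.** Because exp(−p) > 1 − p for every p > 0, retention is always below p. No date results.
- **Years.** The direction depends on the time left. Retention is below p only when the remaining time exceeds −ln(p)/p years: 1.386 years (72 weeks) at p = 0.50 and 0.510 years (27 weeks) at p = 0.70. With 124 weeks left it is too low at all four values. With 20 weeks left it is too high at 0.70 and 0.50.
- **Weeks.** Retention is near zero unless only a week or two remains.

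**Effect over visits.** For the interval unit, p = 0.95, a stop at Week 140 and a constant hazard, imputed retention is exp(−0.95f) and the Cox value is 0.95^f, with f = (visit − 140)/124:

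| Visit | f | Imputed | Cox |
|---|---|---|---|
| Week 152 | 0.097 | 0.91 | 0.995 |
| Week 184 | 0.355 | 0.71 | 0.98 |
| Week 216 | 0.613 | 0.56 | 0.97 |
| Week 248 | 0.871 | 0.44 | 0.96 |

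For a stop at Week 244 and the same p, f at Week 248 is 4/20 = 0.2. Imputed retention is then exp(−0.19) = 0.83 against 0.95^0.2 = 0.99. At a given visit the gap is large for early stops and small for late ones.

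**Effect on response.** If 60% of adherent subjects respond (assumed) and p = 0.90, these subjects should contribute 0.60 × 0.90 = 0.54 at Week 264. The interval unit gives 0.60 × 0.407 = 0.24, and the rule retained if X < 1 gives 0.60 × 0.593 = 0.36.

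**Check of the replacements.** In two million draws per value of p (stop at Week 140, Week 248, constant hazard), inverting the conditional survival curve with a uniform draw gave 0.956/0.913/0.733/0.547. An exponential time with rate −ln(p)/124 per week gave 0.956/0.912/0.733/0.546. The Cox values are 0.956/0.912/0.733/0.547.

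**The case against.** The text is incomplete rather than provably wrong in execution. A programmer could add a rule that works: calling the subject on treatment when X > −ln(p)/p gives exp(ln p) = p exactly. That stands, but the SAP does not state the rule, and it yields status at t_EoTrt only, with no date for the earlier visits. Another possible construction places the draw on the cumulative-hazard scale, which gives retention p^p: 0.95, 0.91, 0.78 and 0.71 at the four assumed values. That is close to p at 0.90 and above and too high below. It too needs a scale that the SAP does not mention.

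The analysis is also only a sensitivity analysis. SAP 5.6.1.1.2 says openly that its scenarios are hypothetical and some extreme, no testing is specified (SAP Section 2), and observed cases is the primary analysis of these endpoints. All of this stands and limits the consequence.

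A reader might go further and infer that the lower bound is invalid. The documents do not support that in general. Where dropout is overstated, the result is still a lower bound, only looser than intended; only where dropout is understated does it sit too high. Even then it cannot exceed hMI apart from simulation noise, because imputed dropout only turns responders into non-responders on top of the same 2-step imputation. Nor can it be inferred that reported results are wrong, since the program is not visible and may differ from the wording.

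**Conclusion.** The point holds as a specification error in one sensitivity analysis and should be fixed. Taken literally, the sentence uses a retention probability as a hazard rate. The natural readings fail to return p, and the mNRI-MI-Hyp bound for IGA 0/1 and EASI75 cannot be reproduced from the SAP.

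The possible size is substantial: at an assumed p of 0.95, retention at Week 264 is 0.39 or 0.61 under the two simplest readings. The direction is not fixed. It depends on the reading, on p and, for year units, on the time remaining. The figures rest on assumed values of p and assumed stopping weeks, and the by-visit comparison also on a constant hazard. No overall change in the response rate can be stated.

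Observed cases, hMI and the primary safety endpoint are unaffected.

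**What to change.** In SAP 5.6.1.1.2.3:

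1. Replace the exponential draw with U ~ Uniform(0,1) and solve S(T)/S(t_ICE) = U for the LoE/AE discontinuation time T. If T ≤ t_EoTrt, the subject is a non-responder at visits after T; otherwise the subject is retained. An exponential time with rate −ln(p)/(t_EoTrt − t_ICE) also returns p at t_EoTrt, but it matches the Cox curve at earlier visits only under a constant hazard.
2. State that the Cox event is a permanent stop of IMP for LoE or AE, censored at treatment completion and at withdrawal for any other reason.
3. Align the pandemic clause with the intercurrent events in SAP 5.2 and the scope in SAP 5.6.1.1.2.2.
4. Check the program against the corrected text before database lock.

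The cost is a few lines of SAP text and code, with no effect on data collection. Drawing the Cox parameters afresh for each imputation, so that Rubin's rule carries their uncertainty, is an optional and separate refinement.

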5.6.1.1.3 Supplemental analysis

To evaluate the efficacy of tralokinumab given as continuous treatment, re-treatment, or introduced for the first time in tralokinumab-naïve subjects, each specified analysis above will also be done within each of the tralokinumab naïve, re-treated, continuously treated, and washed-out sub-populations.

5.6.2 Analysis of other endpoints

Due to the changed visit structure introduced in May 2021, some endpoints have been specified as combining data from 2 possible visits, e.g., Change in DLQI/CDLQI score from baseline to Weeks 80-88. The rule for handling these endpoints will be to calculate the endpoint based on the first existing data. Hence, where a subject had an assessment at both Week 80 and Week 88, the Week 80 assessment (corresponding to approximately $1\frac{1}{2}$ years) will be prioritised for the Week 80-88 endpoint evaluation. Likewise, the Week 128 assessment (~ $2\frac{1}{2}$ years) will be prioritised for the Week 128-136 endpoint evaluation.

The DLQI score will be presented for subjects from the parent trials LP0162-1325, -1326, -1339, -1341, -1343, and -1346. The CDLQI score will be presented for subjects from the parent trial LP0162-1334. As subjects from the parent trial LP0162-1342 did not have POEM, DLQI, or EQ-5D-5L assessments in the parent trial, the change from baseline is not applicable. As subjects from the parent trials LP0162-1334 and -1343 did not have EQ-5D-5L assessments in the parent trials LP0162-1334 and -1343 did not have EQ-5D-5L assessments in the parent trials LP0162-1334 and -1343 did not have EQ-5D-5L assessments in the parent trials LP0162-1334 and -1343 did not have EQ-5D-5L assessments in the parent trial, the change from baseline is not applicable. Changes from baseline will not be presented for subjects from the parent trial TRA-WEI-0015-I since data from this investigator-initiated trial have not been transferred to LEO Pharma (see the CTP Section 14.2).

5.6.2.1 Continuous endpoints

5.6.2.1.1 Primary analysis

As observed according to general principles.

Figures will be made with the median and 1st and 3rd quartiles and an table appended showing the number of subjects with observed data at each visit.

5.6.2.1.2 Sensitivity analysis

No sensitivity analysis will be made for continuous other endpoints.

5.6.2.1.3 Supplemental analysis

To evaluate the efficacy of tralokinumab given as continuous treatment, re-treatment, or introduced for the first time in tralokinumab-naïve subjects, each specified analysis above will also be done by tralokinumab naïve, re-treated, continuously treated, and washed-out sub-populations.

5.6.2.2 Proportion of response over time endpoints

5.6.2.2.1 Primary analysis

The proportion of response over time will be estimated by the AUC over daily responses estimated through linear interpolation between observed assessments made at scheduled visits. The analysis will calculate the mean proportion (assumed continuous) and 95% Wald CI appended, with the standard deviation, median, 1st and 3rd quartiles, and minimum and maximum values appended as well.

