9.5 Rescue treatment

If medically necessary (that is, to control intolerable AD symptoms), rescue treatment for AD may be provided to trial subjects at the discretion of the investigator. If possible, investigators should attempt to limit the first step of rescue therapy to topical medications, and escalate to systemic medications only for subjects who do not respond adequately after at least 14 days of topical treatment.

Subjects who receive topical rescue treatment (higher potency TCS: US class <4 or Europe class >3) will continue treatment with IMP. If TCS are used as rescue treatment, the subject should be monitored for signs of local or systemic TCS toxicity, and the safety and appropriateness of continued use should be supervised by site staff.

If a subject receives rescue treatment with systemic corticosteroids or non-steroidal systemic immunosuppressive drugs (for example, cyclosporine, methotrexate, mycophenolate mofetil, azathioprine), treatment with IMP will be immediately discontinued (see Section 10.2.3). After the treatment with these medications is completed, IMP may be resumed if deemed appropriate by the investigator, but not sooner than 5 half-lives after the last dose of systemic rescue treatment. The use of biological rescue treatment will be disallowed for the entire trial duration.

Investigators should make every attempt to conduct efficacy and safety assessments (at least disease severity scores [IGA and EASI], concomitant medications/procedures, and AEs) immediately before administering any rescue treatment. An unscheduled visit may be used for this purpose, if necessary.

Page 67 of 187

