10.3 Early termination assessments

Withdrawal from trial

Subjects withdrawn from the trial for any reason should attend an early termination visit as soon as possible after the last administration of IMP and should return to the trial site for a safety follow-up visit after last administration of IMP as specified in Section 7.1.4. See the schedule of trial procedures (Section 4) for data to be collected at an early termination visit. The investigator will review any AEs, which will be followed up according to Section 13.7, if the subject agrees. An EOT (end of treatment) form and an end of trial form must be completed as specified in Section 11.8. No EOT visit is to be done for subjects who are withdrawn from trial.

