14.3.6 Other endpoints

Changes from baseline in EASI score and SCORAD will be presented as number of observations (N), mean, standard deviation (SD), median, minimum, and maximum at each assessment visit. The baseline scores used will be those from the parent trial.

The changes from baseline in EASI score and SCORAD will be presented for the FAS as well as for the observed cases.

3 endpoints addressing treatment effect during the treatment period will be included:

- Proportion of time with EASI75 after first occurrence of EASI75 during treatment.
- Proportion of time with EASI50 after first occurrence of EASI50 during treatment.
- Proportion of time with IGA 0/1 after first occurrence of IGA 0/1 during treatment.

The proportion of time with EASI75 for an individual subject will be calculated as the time with EASI75 (that is, the sum of time intervals with EASI75) divided by the observation period after first occurrence of EASI75. The time intervals in which EASI75 is observed at the start of the interval will be accumulated and normalised with the total treatment time from first EASI assessment with EASI75 until end of treatment.

The proportion of time with EASI50 and with IGA = 0/1 after first occurrence during treatment will be determined using the same principle as for the proportion of time with EASI75.

These 'proportion of time' endpoints will each be presented as number of observations (N), mean, SD, median, minimum, and maximum. The group mean comprising the summed nominators (of time) divided by the summed denominators will further be presented.

As the frequency of site visits is reduced after May 2021, a sensitivity analysis excluding data captured after May 2021 will be performed for the 'proportion of time' endpoints. For exploratory purposes, the proportion of subjects achieving EASI75 will be plotted versus the proportion of time with EASI75 (ranging from 0–100% of the observation period after first occurrence of EASI75). Similar plots for EASI50 and IGA 0/1 will be shown in the same graph.

The results for the endpoints described in this section will be presented for the total cohort of subjects and by tralokinumab-naïve/re-treated/continuously treated subjects. For the re-treated

and continuously treated subjects, the results will further be divided by responder/non-responder in the parent trial (clinical response as defined in Section 14.3.5).

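### SAP 5.6.2.2.1 leaves unscheduled pre-rescue IGA/EASI scores out of the proportion-of-time endpoints, does not say whether early termination scores count, and no sensitivity analysis would show the effect

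*SAP*

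**What the plan says.** SAP 5.6.2.2.1 defines the proportion of response over time as the "AUC over daily responses estimated through linear interpolation between observed assessments made at scheduled visits". The SAP does not define a scheduled visit, map early termination to one, or say where the observation window ends. SAP 5.6.2.2.2 defines no sensitivity analyses. SAP 5.6.2.2.3 adds a threshold curve and a split by trial period. For potentially clinically significant vital signs and laboratory values (SAP 5.8.2, 5.8.4), by contrast, the SAP expressly brings in unscheduled samples.

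Protocol 14.3.6 describes the same endpoints differently: "The time intervals in which EASI75 is observed at the start of the interval will be accumulated", and the sum is "normalised with the total treatment time from first EASI assessment with EASI75 until end of treatment". It says nothing either way about unscheduled scores. It also plans a sensitivity analysis without post-May-2021 data, because site visits become less frequent then. SAP Panel 5 lists two changes, both to protocol 14.3.5 and none to 14.3.6.

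On collection, protocol 9.5, 11.1 and the footnotes to Panels 4 and 5 ask investigators to make every attempt to score IGA and EASI immediately before rescue: "An unscheduled visit may be used for this purpose, if necessary". Also in 9.5: "Subjects who receive topical rescue treatment (higher potency TCS: US class <4 or Europe class >3) will continue treatment with IMP". SAP 5.2 lists treatment completion and permanent discontinuation as intercurrent events, but not rescue. For withdrawals, protocol 10.3 says: "Subjects withdrawn from the trial for any reason should attend an early termination visit as soon as possible after the last administration of IMP", and "No EOT visit is to be done for subjects who are withdrawn from trial". Panels 4 and 5 mark IGA and EASI at both the unscheduled and the early termination visit.

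**The concern.** These endpoints describe how durable disease control is. A score taken just before rescue records a time when control was lost. If it falls at an unscheduled visit, it does not reach the endpoint, and rescue has no other route in: treatment time runs on through topical rescue, and rescue is not an intercurrent event. The next scheduled score may also come after higher-potency topical steroid has worked. With up to 16 weeks between efficacy visits, a whole flare can pass between two responding scores and be counted as response.

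For withdrawn subjects, early termination supplies the only closing efficacy score, and two programmers could treat it differently under the present text. The protocol foresaw that sparser visits might affect these endpoints and planned a check. The SAP carries no such check and does not say why. A reader of the durability result could not tell how much it depends on the scores left out.

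**Working it through.** The plan states no expected value, rate or sample size for these endpoints, so there is no figure to reproduce. What can be checked is how the SAP rule behaves with and without an off-schedule score.

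**Inputs from the documents.** Efficacy visits after Week 24 are 16 weeks apart on the post-May-2021 schedule (Panel 5: Weeks 24, 40, 56 and so on) and 8 weeks apart on the earlier one (Panels 3 and 4). EASI75 is judged against the parent-trial baseline.

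**Assumptions.** Parent baseline EASI 32, so the EASI75 threshold is 32 × 0.25 = 8. EASI is 4 at responding visits. Flare and early termination scores are as shown.

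**1. Flare scored at an unscheduled visit between two responding visits.** With scheduled scores only, EASI stays at 4, so 100% of the gap is in response. If a score F is added, the share of the gap in response is (8 − 4)/(F − 4), wherever in the gap the score falls and whatever the gap length:

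| F | Share in response | Weeks out of response, 16-week gap |
|---|---|---|
| 12 | 4/8 = 50% | 8.0 |
| 16 | 4/12 = 33% | 10.7 |
| 24 | 4/20 = 20% | 12.8 |

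**2. Against a known flare length.** If the flare really lasted 2 or 4 weeks of a 16-week gap, true response is 1 − 2/16 = 87.5% or 1 − 4/16 = 75%. Scheduled-only is then 12.5 or 25 points too high for that gap. With F = 16, including the score is 54 or 42 points too low (87.5 − 33.3; 75 − 33.3). Inclusion comes closer to the truth only if the flare lasted more than half the weeks in the last column: 4.0, 5.3 or 6.4 weeks.

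**3. Early termination.** Take EASI 4 at two visits 16 weeks apart, then an early termination score. Without that score the result is 100%. With it:

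- EASI 12, 4 weeks later: (16 + 2)/20 = 90%
- EASI 12, 12 weeks later: (16 + 6)/28 = 79%
- EASI 20, 4 weeks later: (16 + 1)/20 = 85%
- EASI 20, 12 weeks later: (16 + 3)/28 = 68%

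The reverse also occurs. If the last scheduled EASI is 12 and early termination EASI is 0 twelve weeks later, omission gives 8/16 = 50% and inclusion gives (8 + 8)/28 = 57%.

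**4. Cohort mean.** Suppose a share q of subjects has one flare with F = 16 in a 16-week gap. The two versions then differ by q × 10.67/T, where T is weeks observed. For q from 5% to 40%, that is 0.2 to 1.7 points at T = 248 and 0.5 to 4.1 points at T = 104. This is the distance between two rules, not a bias. Against a true flare of d weeks, the overstatement is q × d/T: 0.04 to 0.32 points for d = 2 and T = 248, and 0.19 to 1.54 points for d = 4 and T = 104. The values of q and d are assumptions.

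**The case against.** The strongest case on the other side is that restricting to scheduled visits is a recognised guard against sampling triggered by the outcome. Unscheduled scores cluster on bad days, and linear interpolation stretches one bad day across much of the gap. Continuous higher-potency topical steroid for more than 4 weeks is a reason for withdrawal (protocol 10.2.1), so a topically rescued flare in a subject who continues is plausibly short. Step 2 shows that including the score can then miss by more than leaving it out. This stands, and it is why the scheduled-visit version should remain primary.

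A reader might infer more than the documents support:

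- **That all pre-rescue scores are lost.** Those taken at scheduled visits are kept.
- **That early termination scores are discarded.** The SAP does not say so. Early termination has its own column in Panels 4 and 5, separate from the unscheduled visit. It lacks a fixed week, but so does EOT, so that test would remove both.
- **That omitted early termination scores are mostly failures.** Protocol 10.3 covers withdrawal for any reason. SAP 5.2 describes withdrawals because the drug became commercially available, and such subjects may leave in response.
- **That protocol 14.3.6 requires the off-schedule scores.** It is silent. Under its start-of-interval rule, a closing score out of response does not take away the responding interval before it: in step 3 that rule gives 100% even with the early termination score.

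The stakes are also limited. These are descriptive other endpoints, no testing is specified (SAP 2), and they do not feed the primary or secondary endpoints. The period split in SAP 5.6.2.2.3 shows later follow-up separately, but by trial week and not by visit schedule, and it uses the same scheduled scores.

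**Conclusion.** The point holds in limited form. Unscheduled pre-rescue IGA/EASI scores do not enter the proportion-of-time endpoints, the handling of early termination scores is unstated, and nothing planned would show the effect of either. For rescued flares between responding visits the likely direction is upward, and there is more room for it after May 2021. Where the neighbouring visits are already out of response, omission changes nothing. For early termination scores the direction varies by subject.

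The size cannot be derived from the documents. The cohort figures above, at most a few percentage points, rest on assumed flare rates, scores and durations. It would be tempting to quote them as the amount by which durability is overstated, but without rescue or unscheduled-visit rates they are illustrations only. The loss of the post-May-2021 sensitivity analysis without an entry in SAP Panel 5 is a separate matter of record and depends on none of these assumptions.

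**What to change.** - **SAP 5.6.2.2.1:** keep the scheduled-visit analysis as primary. State that the early termination score is the closing assessment for withdrawn subjects, as the EOT score is for completers.
- **SAP 5.6.2.2.2:** add a sensitivity analysis that uses every IGA/EASI score in the treatment period, including unscheduled pre-rescue scores, and report it beside the primary result for all three endpoints.
- **Post-May-2021 analysis:** restore the sensitivity analysis of protocol 14.3.6, or list its removal with a reason in SAP Panel 5.

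The cost is a few SAP sentences and one extra run on data already collected, plus the May 2021 run if it is restored. The drawback is that flare-triggered scores joined by straight lines can overstate how long a flare lasted. The all-scores result should therefore be labelled as a check that leans low, not as the better estimate.
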